16.11 Imaging

Imaging scans (e.g., X-ray, ultrasound, computed tomography, magnetic resonance imaging) should be performed for the assessment of infection in subjects with non-blood sites of *Candida* infection. The results of these studies should be documented on the eCRF.

For subjects with fungal diseases where the assessment of outcome is based on imaging, imaging scans must be available at Screening/Treatment Day 1 (prior to study treatment) and performed at EoT. Additional images should be obtained if clinically indicated.

16.12 Serological Testing

The following serological examinations will be performed at Screening/Treatment Day 1 (prior to study treatment) and at the recommended time points below:

• Two β-(1,3)-D-glucan consecutive tests every 72 hours until negative

16.13 Safety Laboratory Tests

Safety laboratory tests (hematology, blood chemistry and urinalysis) will be measured at Screening/Treatment Day 1 (prior to study treatment), at Treatment Days 7 to 10, every 14 days

SCYNEXIS, Inc.	IND #107,521
PROTOCOL SCY-078-305	Version 0.1

thereafter up to EoT if clinically indicated, at EoT, at the Week 6 Follow-up if clinically indicated, and at unscheduled visits if clinically indicated. These may also be done more frequently as follow up to a laboratory abnormality.

The following laboratory parameters will be determined:

Hematology

• White blood cell (WBC) count

• Red blood cell (RBC) count

HemoglobinHematocrit

- Platelet count
- Differential WBC count will include percentages for segmented neutrophils, lymphocytes, monocytes, eosinophils and basophils, and absolute counts for neutrophils, lymphocytes, atypical lymphocytes, monocytes, eosinophils and basophils.

Blood Chemistry

- Sodium
- Potassium
- Alkaline Phosphatase
- Chloride
- Blood urea nitrogen (BUN)
- Creatinine
- Total creatine phosphokinase (CPK)
- Aspartate aminotransferase (AST/SGOT)
- Alanine aminotransferase (ALT/SGPT)
- Gamma glutamyl transferase (GGT)
- Lactate dehydrogenase (LDH)
- Bilirubin (total, direct, and indirect)
- Total protein

Coagulation test

- Prothrombin time (PT)
- Activated partial thromboplastin (aPTT)
- Thrombin time (TT)
- D-dimer

- Glucose
- Albumin

- Appearance (clarity, color)
- Specific gravity
- ∎ pH
- Blood
- Bilirubin

- Glucose
- Ketones
- Protein
- Leukocytes
- Urobilinogen

Reflex Microscopic Evaluation

- Bacteria

MucousRBCWBC

- CastsCrystals
- Epithelial cells

16.14 Pharmacokinetic Sample Collection (PK Subset Only)

PK testing will be conducted for subjects who give their consent to participate in the PK portion of the study (the PK Subset). Up to three (3) blood samples will be collected at the following visits and sampling windows: Treatment Day 2 (one sample collected anytime post dosing), Treatment Days 3 to 5 (one sample collected predose on any of these days) and Treatment Days 7 to 10 (one sample collected predose on any of these days).

On PK sampling days, the investigator must record the dosing times and sample collection times on the eCRF and on the subject's medical record.

Procedures for collecting, storing, and shipping plasma samples for PK are described in the study PK Manual. The sparse samples collected in this study will be analyzed using Population PK (Pop PK) analysis methods to estimate PK parameters (C_{max}, AUC, clearance/fraction absorbed [CL/F]) as applicable.

Further analysis of possible metabolites may be performed.

16.15 Efficacy Assessment

Efficacy will be assessed primarily in terms of global success at EoT as determined by the DMC. Complete global response, partial global response, stable disease and progressive disease as determined by the DMC and global success, clinical success and mycological success as determined by the investigator will also be assessed at EoT.

The following study procedures will be performed to assess treatment outcome:

- Clinical signs and symptoms of candidiasis (Section 16.9)
- Radiological assessments including esophagoscopy and other imaging scans, as applicable (e.g., X-ray, ultrasound, CT and MRI) (Section 16.11).
- Mycological testing (fungal cultures) (Section 16.10.)
- Serological testing (β-(1,3)-D glucan) (Section 16.12)

Efficacy assessments will also include recurrence (after EoT) and survival. Recurrence will be assessed by measuring recurrence of the baseline fungal infection 42 days after EoT (Week 6 FU). Survival will be determined on Day 42 and Day 84 (42 and 84 days after Screening/Treatment Day 1 [first dose of study drug]). This can be an in-person visit or a phone contact, and will document subject status only (alive or deceased). If subject is deceased, the relationship to the fungal infection will be recorded.

See Section 20.7.1 for a detailed description of efficacy outcomes.

16.16 Study Drug Dispensing, Collection and Treatment Compliance Evaluation

For subjects who are not hospitalized, the study drug will be dispensed at Screening/Treatment Day 1. Subjects who are hospitalized and are later discharged from hospital will be dispensed their study drug at the time they are discharged. Study drug will be dispensed at each Treatment visit and will be supplied in bottles containing enough study drug to last until the next study visit. Study drug will be collected for treatment compliance evaluation on Treatment Days 3 to 5, Treatment Days 7 to 10, every 14 days thereafter up to EoT and at unscheduled visits prior to EoT (see Section 14.5 for further details).

16.17 Study Drug Dosing

All enrolled subjects will receive an initial oral loading dose of 750 mg of SCY-078 (3 tablets of 250 mg) BID during the first 2 days of treatment and then subsequent oral doses of 750 mg QD for up to 90 days. Oral treatment may be given on an inpatient or outpatient basis, as needed, and for as long as is clinically indicated, at the investigator's discretion, but in no event for more than a total of 90 days of antifungal treatment.

For subjects who are unable to take oral medications, tablets may be crushed and administered with approximately 8 oz./240 mL of water via an NG or PEG tube. The tube should be closed at least one hour before drug administration and be flushed with approximately 8 oz./240 mL of water before and after drug administration.

Further details of the study treatment and dietary requirements for treatment administration are provided in Section 14.1 and Section 14.2, respectively.

16.18 Subject Diary Dispensing, Collection and Review

Non-hospitalized subjects will complete a subject diary up to their EoT visit. The subjects will record the date/time of study medication dosing, daily symptoms, other medical concerns or complaints and concomitant medications.

Subject diaries will be dispensed at Screening/Treatment Day 1 and will be reviewed on Treatment Days 7 to 10, every 14 days thereafter up to EoT, at EoT and at any unscheduled visit conducted prior to EoT. Subject diaries will be collected at EoT.

16.19 Prior and Concomitant Medication Review

All medications (including prescription and OTC medications, supplements, and herbal products) taken from 28 days before Screening/Treatment Day 1 through the EoT will be recorded on the eCRF. Only the use of antifungal medications, antibiotics for any reason or medications to treat an AE will be recorded after EoT and through the Week 6 Follow-up visit. See Section 15.0 for prohibited medications, medications to be administered with caution and further details for non-study treatments.

16.20 Adverse Event Monitoring

AEs will be collected and evaluated from the time the informed consent is signed through the EoT. After the EoT and up to the last observation in the study (Week 6 Follow-up), new AEs will be collected only if deemed related to the study drug, if they are serious adverse events (SAEs), or if they are related to a fungal infection.

See Section 18.0 for details regarding safety assessment and monitoring.

17.0 Study Schedule

Detailed schedules of all study visits and procedures are presented in the Schedules of Visits and Procedures (Table 1 and Table 2).

PROCEDURE	Visit 1	Visit 2	Visit 3	Visit 4	Visit 5-10	ЕоТ	Week 6	Unscheduled
VISIT	Screening/	(DV Subset only)	Treatment	I reatment	Every 14 days	Day	Follow-up	V 18108/
	(Resoline)	(PK Subset only)	Days 5 10 5	Days / to 10	Treatment		(0 weeks	
Days (allowable window)	Day -1 to Day 1				$\pm 2 \text{ days}$	± 2 days	$\pm 2 \text{ days}$	
Informed Consent	Xa							
Inclusion/Exclusion Criteria	Xa							
Subject Enrollment and ID Assignment	Xa							
Medical History and Demographics	X ^a							
General Physical exam	X ^a					Х	Х	
Vital Signs	X ^a					Х		If applic.
12-Lead ECG	X ^a					Х		If applic.
Pregnancy Test	X ^a					Х		
Targeted Physical Exam including Clinical Evaluation of Signs and Symptoms of Infection	Xª		Х	Х	Х	Х	х	
All Mycological Testing	Xa		If applic.	If applic.	If applic.	If applic.	If applic.	If applic.
Imaging (if applicable)	Xa		If applic.	If applic.	If applic.	X	If applic.	If applic.
Serological Testing	Xa		If applic.	If applic.	If applic.	Х	If applic.	If applic.
Clinical Safety Laboratory Assessments (hematology, blood chemistry, urinalysis)	Xa			Х	If applic.	Х	If applic.	If applic.
Pharmacokinetic Assessments (PK Subset only) ^b		Х	Х	Х				
Efficacy Assessment						Х	Х	
Study Drug Dispensing	Х		Х	Х	Х			
Study Drug Dosing ^c	Х					X		
Study Drug Collection and Treatment Compliance Evaluation		Х	Х	Х	Х	Х		Х
Subject Diary Dispensing, Collection and Review	X			X	Х	Х		X
Prior and Concomitant Medication Review	Х	Х	Х	Х	Х	Х	Х	Х
Adverse Event Monitoring	Х	Х	Х	Х	Х	Х	X	Х

 Table 1:
 Schedule of Treatment Visits and Procedures (Study SCY-078-305)

06 OCT 2017

PROCEDURE	Visit 1	Visit 2	Visit 3	Visit 4	Visit 5-10	ЕоТ	Week 6	Unscheduled
Visit	Screening/	Treatment Day 2	Treatment	Treatment	Every 14 days	Day	Follow-up	Visits/
	Treatment Day 1	(PK Subset only)	Days 3 to 5	Days 7 to 10	during		(6 weeks	
	(Baseline)				Treatment		after EoT)	
Days (allowable window)	Day -1 to Day 1				$\pm 2 \text{ days}$	$\pm 2 \text{ days}$	$\pm 2 \text{ days}$	

Abbreviations: AE=adverse event; applic.= applicable; ECG=electrocardiogram; EoT=end of treatment; PK = pharmacokinetic(s).

a. Conducted prior to first study drug dosing

b. PK testing will be conducted for subjects who give their consent to participate in the PK portion of the study (the PK Subset). Sparse PK samples for Population PK analysis will be collected at the following visits and sampling windows: on Treatment Day 2 (one sample collected anytime post dosing); between Treatment Days 3 to 5 (one sample collected predose on any of these days) and between Treatment Days 7 to 10 (one sample collected predose). The time of dosing and sample collection must be recorded on the subject diary and eCRF.

c. All enrolled subjects will receive an initial oral loading dose of 750 mg of SCY-078 (3 tablets of 250 mg) BID during the first 2 days of treatment and then subsequent oral doses of 750 mg QD for up to 90 days.

PROCEDURE Visit	Visit/contact Survival Day 42	Visit/contact Survival Day 84
Days (allowable window)	± 2	± 2
Subject Status (alive/ deceased)	Х	Х

Table 2Schedule of Survival Visits and Procedures (Study
SCY-078-305)

18.0 Safety Assessments and Monitoring

18.1 Definition of an Adverse Event

An AE is any untoward medical occurrence associated with the use of a drug in humans, whether or not considered drug related. An AE can therefore be any unfavorable and unintended sign (including an abnormal laboratory finding), symptom or disease temporally associated with the use of a study drug/study intervention, whether or not related to the study drug/study intervention.

Any laboratory abnormality that is deemed to be clinically significant in the opinion of the investigator will be considered an AE and should be recorded in the eCRF, whether or not it is related to the study drug.

Stable chronic conditions that are present prior to clinical trial enrollment and do not worsen are not considered AEs and will be accounted for in the subject's medical history.

The following can be considered AEs:

- An exacerbation of a pre-existing illness
- An increase in frequency or intensity of a pre-existing episodic event or condition
- A condition detected or diagnosed after the initiation of treatment with study medication, even though it may have been present prior to the start of the study
- Continuous persistent disease or symptoms present at Baseline that worsen after signing the informed consent or following the initiation of treatment with study medication

The following are **not** considered AEs:

- Medical or surgical procedures (e.g., surgery, endoscopy, tooth extraction or transfusion); the condition that leads to the procedure is an AE
- Pre-existing disease or conditions present or detected at the start of the study that do not worsen
- Situations where an untoward medical occurrence has not occurred (e.g., hospitalizations for cosmetic surgery or elective surgery or social/convenience admissions)

• The disease being studied or signs or symptoms associated with the disease, unless more severe than expected for the subject's condition or a worsening of the disease being studied

18.2 Definition of a Serious Adverse Event

A SAE is defined as an AE meeting one of the following outcomes:

- Death
- Life-threatening event
- Inpatient hospitalization or prolongation of existing hospitalization
- Persistent or significant disability/incapacity or substantial disruption of the ability to conduct normal life functions
- Congenital anomaly or birth defect

Any other important medical event that may not result in one of the above outcomes may be considered a SAE when, based upon appropriate medical judgment, the event may jeopardize the participant and may require medical or surgical intervention to prevent one of the outcomes listed above.

A life-threatening AE is any AE that places the subject, in the view of the investigator, at immediate risk of death from the AE as it occurred. It does not include an AE that, had it occurred in a more severe form, might have caused death.

18.3 Events of Clinical Interest

The following are considered events of clinical interest (ECIs), and must be reported by the site when it becomes aware of the ECI:

- QTc >500 ms or a >60-ms change from Baseline, confirmed by repeat testing
- ALT or AST >8 x ULN, if new compared to Baseline, confirmed by repeat testing
- ALT or AST >5 x ULN for more than 2 weeks and if new compared to Baseline, confirmed by repeat testing
- ALT or AST >3 x ULN and either total bilirubin >2 x ULN or INR >1.5 and if new compared to Baseline, confirmed by repeat testing
- ALT or AST >3 x ULN, confirmed by repeat testing, with the appearance of fatigue, nausea, vomiting, right upper quadrant pain or tenderness, fever, rash, and/or eosinophilia (>5%)]

18.4 Overdose

This refers to the administration of a quantity of a medicinal product given per administration or cumulatively, which is above the maximum recommended dose according to the authorized product information.

An overdose can occur if a subject has taken, accidentally or intentionally, a drug administered in a dose exceeding the protocol-specified dose. An overdose must be reported within 24 hours of the site becoming aware of the overdose if such overdose occurs with an associated SAE. If an overdose occurs without an associated SAE, the overdose must be reported within 5 working days and documented in the subject diary and in the subject medical record.

18.5 Pregnancy

Female subjects who become pregnant should be immediately discontinued from the study and followed up to determine the outcome of the pregnancy. The pregnancy must be reported to the Sponsor within 24 hours of the site becoming aware of the pregnancy. If the pregnancy ends for any reason before the anticipated date, the investigator should notify the Sponsor. At the completion of the pregnancy, the investigator will document the outcome of the pregnancy. If the outcome of the pregnancy meets the criteria for immediate classification as an SAE (i.e., postpartum complication, spontaneous abortion, stillbirth, neonatal death or congenital anomaly), the investigator should follow the procedures for reporting an SAE.

18.6 Unexpected Adverse Event

An AE is considered "unexpected" if it is not listed in the IB or is of greater specificity or severity than those that have been observed with the particular study drug being tested. For example, under this definition, hepatic necrosis would be unexpected (by virtue of greater severity) if the IB referred only to elevated hepatic enzymes or hepatitis. Similarly, cerebral thromboembolism and cerebral vasculitis would be unexpected (by virtue of greater specificity) if the IB listed only cerebral vascular accidents. "Unexpected," as used in this definition, also refers to AEs that are mentioned in the IB as occurring with a class of drugs or as anticipated from the pharmacological properties of the drug but are not specifically mentioned as occurring with the particular drug under investigation.

18.7 Grading of Adverse Events

The severity (or intensity) of an AE refers to the extent to which it affects the subject's daily activities and will be classified by the investigator as mild, moderate or severe using the following criteria:

- Mild: Awareness of sign or symptom, but easily tolerated. Not likely to require medical attention.
- Moderate: Discomfort enough to cause some interference with daily activity. May require medical intervention.
- Severe: Intense enough to disrupt daily activities. Likely requires medical intervention.

Clarification of the difference in meaning between "severe" and "serious"

The term "severe" is often used to describe the intensity (severity) of a specific event (as in mild, moderate or severe myocardial infarction); the event itself, however, may be of relatively minor medical significance (such as severe headache). This is not the same as "serious", which is based on the outcome or action criteria usually associated with events that pose a threat to life or functioning. Seriousness (not severity) serves as a guide for defining regulatory reporting obligations.

18.8 Causality Assessment

The investigator will assess causality (i.e., whether there is a reasonable possibility that the study drug caused the event) for all AEs and SAEs. The relationship will be characterized using the following classification:

- Related: The temporal relationship of the AE with the study drug makes causality possible and cannot be due to another cause such as other drugs, a surgical intervention or an underlying disease.
- Not related: The temporal relationship of the AE with the study drug makes causality improbable and can be due to another cause such as other drugs, a surgical intervention or an underlying disease.

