13.0 Study Population

13.1 Inclusion Criteria

Subjects must fulfill all of the following criteria to be eligible for study admission:

- Subject is a male or female adult ≥18 years of age on the day the study informed consent form (ICF) is signed.
- 2. Subject has a documented candidiasis, including candidemia, caused by *Candida auris*. The subject is also eligible if he/she is receiving IV antifungal therapy for their *C. auris* infection and, in the judgment of the investigator, long-term IV antifungal therapy is not feasible or desirable due to clinical or logistical circumstances.

A documented candidiasis, including candidemia, caused by *Candida auris* is defined as the recovery of *Candida auris* by culture of a sample obtained within the last 7 days.

- 3. Subject is able to tolerate medication orally or through a nasogastric (NG) tube or percutaneous endoscopic gastrostomy (PEG) tube.
- 4. Subject is not pregnant and is highly unlikely to become pregnant or to impregnate a partner since he/she meets at least one of the following criteria:
 - a. Subject is a female subject who is not of reproductive potential and is eligible without requiring the use of contraception. A female subject who is not of reproductive potential is defined as one who: (1) has reached natural menopause (defined as 6 months of spontaneous amenorrhea with serum follicle-stimulating hormone levels in the postmenopausal range as determined by the local laboratory, or 12 months of spontaneous amenorrhea); (2) is 6 weeks' post-surgical bilateral oophorectomy with or without hysterectomy; or (3) has undergone bilateral tubal ligation. Spontaneous amenorrhea does not include cases for which there is an underlying disease that causes amenorrhea (i.e., anorexia nervosa).
 - b. Subject is a male subject who is not of reproductive potential and is eligible without requiring the use of contraception. A male subject who is not of reproductive potential is defined as one whom has undergone a successful vasectomy. A successful vasectomy is defined as (1) microscopic documentation of azoospermia, or (2) a vasectomy more than 2 years ago with no resultant pregnancy despite sexual activity post vasectomy.

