8.1 Adverse Events

All AE summaries will be restricted to treatment-emergent AEs (TEAEs) only. A TEAE is defined as any event not present before exposure to study drug or any event already present that worsens in either intensity or frequency after exposure to study drug.

For the purpose of inclusion in TEAE tables, incomplete AE start and end dates will be imputed as follows:

Missing onset dates (where UK and UNK indicate unknown or missing day and month respectively):

- UK-MMM-YYYY: If the month and year are different from the month and year of the date of first dose, assume 01-MMM-YYYY. If the month and year are the same as the month and year for the date of first dose, and the end date (after any imputation) is on or after the date of first dose, then assume the date of first dose. If the month and year are the same as the date of first dose, and the end date (after any imputation) is prior to the date of first dose, then assume the end date for the start date.
- DD-UNK-YYYY/UK-UNK-YYYY: If the year is different from the year of the date of first dose, assume 01-JAN-YYYY of the collected year. If the year is the same as the date of first dose year, and the end date (after any imputation) is on or after the date of first dose, then assume the date of first dose. If the year is the same as the date of first dose, and the end date (after any imputation) is prior to the date of first dose, then assume the end date.

Missing end dates (where UK and UNK indicate unknown or missing day and month respectively):

- UK-MMM-YYYY: Assume the last day of the month;
- DD-UNK-YYYY/UK-UNK-YYYY: Assume 31-DEC-YYYY.

All adverse events will be classified by SOC and PT according to the Medical Dictionary for Regulatory Activities (MedDRA, March 2023 Version). An overview summary of the number and percentage of subjects with any TEAE, serious TEAE, treatment-related TEAE, treatment-related serious TEAE, TEAE leading to study treatment discontinuation, TEAE leading to study discontinuation, and AE leading to death will be provided.

All AEs will be presented in a listing.

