8.1.2 Related Adverse Event to Study Treatment

A summary of related TEAEs to study treatment will be presented in a table. The investigator will provide an assessment of the relationship of the event to the study treatment. Related AEs are those reported as "Possibly Related", "Probably Related", or "Related". If a subject reports multiple occurrences of the same TEAE, only the most closely related occurrence will be presented. Treatment-emergent AEs that are missing a relationship will be considered "Related" and be presented in the summary table but will be presented in the data listing with a missing relationship. Percentages will be calculated based on the number of subjects in the safety population.

The TEAE data will be categorized and presented by SOC and PT in a manner similar to that described in Section 8.1.1.

Related treatment-emergent SAEs to study treatment will also be presented in a table. Treatmentemergent SAEs that are missing a relationship will be presented in the table as "Related" but will be presented in the data listing with a missing relationship.

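### Protocol 18.8 asks whether drug causation is reasonably possible, yet bars Related when another cause exists; SAP 8.1.2 counts two levels that neither document defines

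*Protocol*

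**What the plan says.** Protocol 18.8 has the investigator judge, for every AE and SAE, "whether there is a reasonable possibility that the study drug caused the event". Two classes follow. Related applies when the temporal relationship "makes causality possible and cannot be due to another cause such as other drugs, a surgical intervention or an underlying disease". Not related applies when the temporal relationship "makes causality improbable and can be due to another cause", with the same examples of other causes. There is no third class.

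SAP 8.1.2 also relies on the investigator's assessment, but with different levels: "Related AEs are those reported as 'Possibly Related', 'Probably Related', or 'Related". When the same TEAE recurs in a subject, "only the most closely related occurrence will be presented". For gaps, "Treatment-emergent AEs that are missing a relationship will be considered 'Related' and be presented in the summary table".

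The class is used in these places:
- **Overview (SAP 8.1):** the number and percentage of subjects "with any TEAE, serious TEAE, treatment-related TEAE, treatment-related serious TEAE, TEAE leading to study treatment discontinuation", followed by lines for study discontinuation and death.
- **Tables (SAP 8.1.1 to 8.1.3):** related TEAEs, related serious TEAEs, and related TEAEs by severity.
- **Collection (Protocol 16.20 and 18.9):** after EoT a new AE is recorded only if it is considered drug-related, is serious, or is related to a fungal infection.

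**The concern.** The opening question and the Related class set different thresholds. The question is met when drug causation is reasonably possible. The class needs every other cause to be ruled out, and other drugs, surgery and underlying disease are named among those causes. Two investigators who both follow 18.8 can code the same event differently, depending on whether they apply the question or the bullet.

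The SAP adds a second mismatch. Its related count includes two levels that 18.8 does not offer, so a reader of the tables cannot tell what threshold lies behind the word related.

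Safety and tolerability is a secondary objective (Protocol 10.2) and the only stated basis for the 30 subjects (Protocol 20.1). Protocol 20.8.2 promises a summary of relationship to treatment. The trial has one arm, so no concurrent comparison of TEAE rates is available to set beside the related-event outputs.

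**Working it through.** The plan gives no figure to reproduce. The check is a comparison of texts and a count of categories.

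**1. Cross-classify the two criteria in Protocol 18.8.** Timing is either possible or improbable, and another cause either can or cannot explain the event: 2 × 2 = 4 combinations.

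| Timing makes causality | Another cause | Class under the bullets |
|---|---|---|
| possible | cannot explain the event | Related |
| possible | can explain the event | none |
| improbable | can explain the event | Not related |
| improbable | cannot explain the event | none |

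The bullets cover 1 + 1 = 2 of the 4, which leaves 4 − 2 = 2 without a class. The second row is the material one, because such an event can satisfy the opening question. The fourth row matters little in practice.

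**2. Compare the levels.** Protocol 18.8 has two: Related and Not related. SAP 8.1.2 counts three as related, plus missing. Of the three, 3 − 1 = 2 are absent from 18.8, and no other section of either document defines them.

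**3. Follow a second-row event into the SAP count.** The eCRF is not among the documents, so both cases stay open.
- *eCRF with the protocol's two levels.* Coded by the opening question, the event is Related and counted. Coded Not related because the Related bullet excludes it, it is not counted. Left blank because neither bullet fits, it is counted under the missing-as-related rule.
- *eCRF with graded levels.* The event is counted if the investigator picks Possibly Related or higher, but the protocol does not say when to do so.

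The same event can thus fall inside or outside the count, which is why neither size nor direction can be derived.

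**4. Count the outputs that use the class.**
- The SAP 8.1 overview lists: any TEAE; serious; treatment-related; treatment-related serious; leading to treatment discontinuation; leading to study discontinuation; leading to death. That is 7 lines, of which 2 use the class.
- Tables: related TEAEs and related serious TEAEs (each named in both 8.1.1 and 8.1.2, counted once here), and related TEAEs by severity (8.1.3). That is 3.

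**5. Check collection.** Through EoT all AEs are collected whatever their class (Protocol 18.9). After EoT, a new second-row event that is neither serious nor related to a fungal infection may go unrecorded. The SAP's missing-as-related rule cannot recover an event that was never entered. If the event was treated, the post-EoT medication record in Protocol 15.1 may show a trace.

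**6. Check what is outside the problem.** Sites report all SAEs within 24 hours whatever the causality (Protocol 18.12). Regulatory submission uses the assessment of the medical monitor or the sponsor (Protocol 18.10). The all-TEAE tables do not use the class for events that were collected.

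**The case against.** The strongest reply is that the problem is one of wording with limited reach. An investigator can take the opening question as the operative one and classify the second-row event without difficulty, and no document shows that anyone applied the strict bullet. The SAP count is formally defined: if the eCRF had only two levels, the extra labels stay empty. The primary endpoint does not use the class, and the only AE percentage named as a secondary endpoint (Protocol 11.2) is that of treatment-emergent events, not related ones. Related counts rest on investigator judgement in controlled trials too.

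Much of this stands, and it limits the weight of the point. It does not remove the conflict. An investigator who follows the opening question departs from the written bullet, and the tables will not show who did so. A defined count is not interpretable if the threshold behind its levels is unknown.

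A reader might infer more than the documents support, in three ways:
- *That competing causes must be frequent because every subject enters with C. auris infection* (Protocol 13.1: "Subject has a documented candidiasis, including candidemia, caused by" that organism). Protocol 18.1 generally keeps the signs and symptoms of the studied disease out of the AE definition unless they worsen or exceed what is expected. After EoT, events related to a fungal infection are collected in any case. The documents give no frequency.
- *That the rule on the most closely related occurrence proves a graded scale.* It also works on two levels, since Related outranks Not related.
- *That the 42 days from EoT to the Week 6 visit, as a share of follow-up, measure the loss.* Such a share describes the restricted collection rule, not the effect of 18.8, and it counts time rather than events.

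**Conclusion.** The point holds. Protocol 18.8 contradicts itself: an event with plausible timing and a competing cause can meet its question and fits neither of its classes. SAP 8.1.2 adds two levels that are undefined in both documents, and nothing elsewhere reconciles them.

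The scope is fixed by the text: 2 of 4 combinations without a class, one of them material; 2 of 7 overview lines; three tables; and the post-EoT collection of new events that are neither serious nor related to a fungal infection. The count of four combinations assumes a literal reading of the two bullets. It would be tempting to conclude that related events are under-counted. The documents do not establish this, because the result depends on the eCRF levels and on how investigators read 18.8, and neither is shown.

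This should be corrected. It does not touch the primary endpoint, site SAE reporting or the all-TEAE tables for collected events.

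**What to change.** - **Protocol 18.8:** define Related as a reasonable possibility that the study drug caused the event, whether or not another cause is also possible, and Not related as no such reasonable possibility.
- **Levels:** use one set in protocol, eCRF and SAP.
- **SAP 8.1.2:** add a sentence stating the levels the eCRF actually offered. Keep the existing collapse rule, including missing counted as related.
- **Study report:** if events were already coded under the current bullets, state this as a limitation of the related-event outputs and of post-EoT collection.

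The cost is two bullets in the protocol, the eCRF completion guideline and one SAP sentence. SAP section 1 allows a SAP amendment before database lock. The downside is that more events may be labelled related, and rewording does not change judgements already made. The SAP cites 2023 coding dictionaries and describes the PK work as closed, so much of the coding may be done. In that case the practical steps are the SAP sentence and the limitation statement.
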